- To investigate the genetic variations in cancer genes, drug target and pathway genes, and other biomarker genes, and correlation with treatment outcomes (optional for subjects; separate informed consent required).

Part 2

- To estimate the efficacy of AMG 655 in combination with AMG 479 using clinical benefit rate (CR, PR, and disease stabilization [SD] \geq 12 weeks, as measured by modified RECIST)

Approved

Study Hypotheses

Part 1: AMG 655 in combination with AMG 479 is safe and tolerated as determined by the incidence of DLT when administered to subjects with advanced, treatment-refractory solid tumors.

Part 2: The combination of AMG 655 with AMG 479 will have an acceptable safety profile and will be associated with at least 3 objective responses out of 15 evaluable subjects in at least 1 cohort (advanced NSCLC [squamous and/or non-squamous histology], CRC, pancreatic cancer, ovarian cancer, and/or sarcoma).

Study Design ([Section 3.1](#))

This is a multi-center, open-label, 2-part phase 1b/2 study of AMG 655 in combination with AMG 479.

Part 1 is a dose escalation segment to identify a dose of AMG 655 in combination with AMG 479 that is safe and tolerable as determined by the incidence of DLT. The maximum dose of AMG 655 planned is 15 mg/kg Q3W. There will be no intra-subject dose escalations in each of the planned dose cohorts.

Part 2 will open once a dose of AMG 655 has been identified that is safe and tolerated based on the incidence of DLT in Part 1 and evaluate the safety and estimate the efficacy (as measured by ORR) of AMG 655 at the dose selected in Part 1 in combination with AMG 479 for the treatment of patients with advanced NSCLC (Cohort 1: non-squamous histology; Cohort 2: squamous histology), CRC (Cohort 3), pancreatic cancer (Cohort 4), ovarian cancer (Cohort 5), and sarcoma (Cohort 6). Enrollment into the 6 cohorts will occur in parallel, independent of one another.

Parts 1 and 2

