AMG 655 and AMG 479 treatment will be administered Q3W until disease progression, intolerable adverse event, death, withdrawal of consent, or administrative decision, for up to 24 months from the date of first study treatment (study day 1). Subjects who have completed 24 months of AMG 655 and/or AMG 479 treatment and who continue to benefit from treatment may be eligible for continued treatment with AMG 655 and/or AMG 479 by extension protocol or as provided for by the local country's regulatory mechanism ([Section 13](#)). Study treatment will cease if a subject experiences progressive disease (PD), death, intolerable adverse event(s), withdraws consent or due to an administrative decision (by the investigator or Amgen).

Radiological imaging (per modified RECIST) will be performed every 6 weeks (\pm 7 days) during the first 6 months of the study, and every 9 weeks (\pm 7 days) thereafter, until subjects develop PD (per modified RECIST) or begin a new cancer treatment. Safety follow-up visits will occur 30 ($+ 7$) days and 60 ($+ 14$) days after the last dose of protocol-specified treatment. Subjects will be contacted every 3 months (\pm 2 weeks) in the long-term follow-up, for up to 36 months from the date of the last subject enrolled, to assess survival.

To mitigate potential safety risks, the first 3 subjects in Part 1 will be enrolled at a rate of \leq 1 subject per week. The study team will review Part 1 dose level cohort data to make recommendations on dose escalation, dose selection and dose stopping. During Part 2 of the study, the study team will review safety data after a total of at least 15 subjects (Interim Analysis [IA] 1) and 45 subjects (IA 2) have been enrolled and have completed 1 cycle of treatment, and additionally as warranted during the conduct of this clinical trial.

The [Study Schema](#) is provided at the end of the Protocol Synopsis section.

Primary and Secondary Endpoints ([Section 10.2](#))

Part 1: The incidence of adverse events and clinical laboratory abnormalities defined as DLT

Part 2: ORR (confirmed CR and PR, by modified RECIST)

Approved

Secondary Endpoints

Part 1

- The incidence of adverse events and laboratory abnormalities not defined as DLT
- The incidence of anti-AMG 655 antibody formation and anti-AMG 479 antibody formation
- PK (C_{max} and C_{min} for AMG 655 and AMG 479)

Part 2

- Time to response
- Duration of response
- PFS
- The incidence of adverse events and laboratory abnormalities

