Statistical Considerations: See [Section 10](#) for details.

Analyses will be presented separately for Part 1 and Part 2 of the study.

Part 1: A sample size of approximately 3 to 6 DLT-evaluable subjects per cohort was selected to identify a dosing regimen of AMG 655 in combination with AMG 479 that is safe and tolerated based on the incidence of DLT. A listing and summary of the incidence of DLT will be presented for each cohort. All other safety data collected in Part 1 of the study will be summarized using appropriate descriptive statistics. The study team will review Part 1 dose level cohort data after at least 3 subjects have completed the DLT window to make recommendations on dose escalation, dose selection and dose stopping.

Part 2

Approximately 90 subjects (15 response-evaluable subjects per cohort [tumor type]) will be enrolled in Part 2. This part of the study will identify tumor types, in which further study of AMG 655 in combination with AMG 479 is warranted, using the following criterion: at least 3 out of 15 subjects have an objective response (an ORR of at least 20%). If 2 or less responders are observed in a given cohort, then all other parameters of clinical benefit (including clinical benefit rate and PFS, within others) and of patient safety will be evaluated to determine if further study is warranted of the AMG 655 and AMG 479 combination in that tumor type. The primary endpoint is ORR. The proportion of subjects with an objective response (confirmed CR or PR by modified RECIST) per local investigator assessment with corresponding 95% exact confidence intervals will be presented for each Part 2 cohort. All safety data collected in part 2 of the study will be summarized per cohort and in aggregate over all cohorts using appropriate descriptive statistics. During Part 2 of the study, the study team will review safety data after a total of at least 15 subjects (Interim Safety Analysis [IA] 1) and 45 subjects (IA 2) have been enrolled and have completed 1 cycle of treatment, and additionally as warranted during the conduct of this clinical trial. Unless safety concerns arise, enrollment will not be stopped during the Part 2 safety reviews.

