The primary analysis of Part 2 will provide the proportion of subjects with an objective response and is planned to occur after all subjects have had the opportunity to complete 4 cycles of treatment. If the recruitment rate is not consistent across cohorts, a piecewise approach to the primary analysis may be taken with the analysis for the quickest recruiting cohorts occurring first.

The final analysis of this study will occur after all subjects have progressed, died, or terminated the study for other reasons.

Sponsor/Licensee: Amgen, Inc.

Approved

Study Design and Treatment Schema

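### Does the review of Part 2 cohorts with 2 or fewer responders need stated reference values and a stated data cut?

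*Combined protocol and SAP*

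**What the plan says.** All references are to the Protocol Synopsis. Its Statistical Considerations entry refers to Section 10 for details, and Section 10 was not part of the text available.

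- **Criterion.** Tumor types for further study are identified by whether "at least 3 out of 15 subjects have an objective response (an ORR of at least 20" percent). The Part 2 hypothesis (Study Hypotheses) also requires an acceptable safety profile.
- **Below the criterion.** The rule opens "If 2 or less responders are observed in a given cohort, then all other parameters of clinical benefit" and continues "including clinical benefit rate and PFS, within others) and of patient safety will be evaluated to determine if further study is warranted".
- **Estimation.** ORR "with corresponding 95% exact confidence intervals will be presented for each Part 2 cohort". The Part 2 primary objective is to estimate efficacy.
- **CBR.** This is an exploratory objective: CR, PR, or stable disease (SD) lasting 12 weeks or more.
- **Scans.** "Radiological imaging (per modified RECIST) will be performed every 6 weeks", give or take 7 days, for the first 6 months.
- **Timing.** The primary analysis "is planned to occur after all subjects have had the opportunity to complete 4 cycles of treatment". If accrual differs between cohorts, "a piecewise approach to the primary analysis may be taken with the analysis for the quickest recruiting cohorts occurring first". The final analysis waits until every subject has progressed, died or left the study.
- **Comparator.** There is no control group.

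**The concern.** Three responders are enough on efficacy but are not required, so a cohort with 0, 1 or 2 can still go forward on a judgment. That judgment leans on CBR and PFS in single-arm cohorts of 15, and the Synopsis names no value against which either is to be read. If the yardstick were chosen after the data were seen, the same result could support going on or stopping.

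Timing adds to this. Four 3-week cycles last exactly as long as the 12 weeks of SD that count as benefit, while the week-12 scan may fall a week early or late. A review held at the earliest primary analysis could therefore miss benefit in the last subjects enrolled. At stake is how far a reader can rely on a verdict that further study is, or is not, warranted in a cohort below 3 of 15.

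**Working it through.** **1. The plan's own figures.** 3/15 = 20%; 6 cohorts × 15 = 90; 9 + 90 = 99 and 18 + 90 = 108. All agree with the Synopsis. It states no alpha, power or null ORR, so there is no error rate to reproduce.

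**2. How often the review is used.** With X ~ Binomial(15, p) and p assumed:

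| True ORR p | P(X ≥ 3) | P(X ≤ 2) |
|---|---|---|
| 5% | 3.6% | 96.4% |
| 10% | 18.4% | 81.6% |
| 20% | 60.2% | 39.8% |

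**3. What the review does to the go probability.** Let q be the chance that a cohort in the review is sent forward (q is not in the documents). Then P(go) = P(X ≥ 3) + q × P(X ≤ 2). At p = 5%:

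- q = 0: 3.6%
- q = 0.1: 0.036 + 0.1 × 0.964 = 13.3% (unrounded inputs)
- q = 0.5: 51.8%
- q = 1: 100%

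Only a binding rule would fix q. A published reference value that leaves the decision to judgment would not.

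**4. What ORR says within the branch.** Exact 95% intervals are 0 to 21.8% for 0/15, 0.2% to 31.9% for 1/15 and 1.7% to 40.5% for 2/15. None excludes 20%. But the plan's criterion is an observed count, not an interval test, and 3/15 itself has an interval of 4.3% to 48.1%. For 0/15 the answer depends on convention: 0.8^15 = 3.5%, and the one-sided 95% upper limit is 1 − 0.05^(1/15) = 18.1%.

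**5. Size of the data-cut effect.** Four cycles are 4 × 21 = 84 days. The week-12 scan falls on days 77 to 91 and the week-18 scan on days 119 to 133, 15 days each. Assumptions:

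- the cut is at day 84 of the last subject, the earliest allowed;
- SD on a scan before day 84 does not count;
- scan days are spread evenly over each window;
- 15 subjects accrue evenly over 91, 182 or 365 days, a spacing of 6.5, 13.0 or 26.1 days (period ÷ 14).

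A subject enrolled L days before the last one has reached day 84 + L. The chance that 12-week SD is not yet documented is:

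- 14/15 at L = 0;
- 8/15 at L = 6.5 (scans on days 84 to 90 are usable);
- 7/15 once the week-12 window has closed;
- from day 119, 7/15 times the share of the week-18 window still to come.

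Expected number of subjects affected:

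- 3 months: 14/15 + 8/15 + 4 × 7/15 + (7/15)(10/15) + (7/15)(4/15) = 3.8
- 6 months: 14/15 + 2 × 7/15 + (7/15)(10/15) = 2.2
- 12 months: 14/15 + 7/15 = 1.4

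A true CBR of 40% then reads on average 0.40 × (15 − 3.8)/15 = 30%, 0.40 × (15 − 2.2)/15 = 34% and 0.40 × (15 − 1.4)/15 = 36%. This treats all benefit as SD; confirmed responders would still count, so the loss is somewhat overstated.

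**The case for a change.** The strongest case for a change is that the branch is the usual path when activity is low, that CBR is only exploratory yet can carry a go decision, and that a paragraph naming reference values and a cut would cost little. It adds that the fastest cohorts, where the cut bites hardest, would be read first under a piecewise analysis. The description is right: the Synopsis does leave both points open, and only the 3/15 part has calculable operating characteristics.

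The step from there to a defect is weaker.

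- **The remedy does not cure the harm.** Unless the review is bound to a cut-off, q in step 3 stays undetermined. Binding it would remove the discretion that a six-cohort screening study reasonably keeps.
- **A reference would often not discriminate.** With 15 subjects, a CBR of, say, 6/15 has an exact 95% interval of 16.3% to 67.7%, so most plausible references would lie inside it.
- **The review is broader than CBR and PFS.** The plan's list is open, and time to response and duration of response are also secondary endpoints.
- **A larger data-cut effect needs stacked assumptions.** If every subject short of day 126 (7, 4 or 2 of the 15) lost the SD credit, 40% would read 21%, 29% or 35%. That needs the earliest cut, non-counting of early scans and an unusable week-12 scan in each of those subjects. It is also an average with benefit spread evenly over subjects, not a bound.
- **A sub-threshold cohort is already visible.** The hypothesis is framed on 3 of 15, and ORR with its exact interval is reported for each cohort.

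**Conclusion.** No change to the plan follows. The Synopsis leaves a gap in detail that the study team can fill sensibly: judge CBR and PFS against what is known for the tumor type, note which subjects are not yet assessable for 12-week SD, and update as later scans arrive. Moving from the earliest cut (day 84 of the last subject) to the end of the week-18 window (day 133) takes 49 days, and the final analysis has complete follow-up in any case.

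The size is this: 96%, 82% or 40% of cohorts reach the review at an assumed true ORR of 5%, 10% or 20%, and the earliest cut would lower a true CBR of 40% to about 30%, 34% or 36% on average under the accrual and scan assumptions in step 5. Neither touches the ORR estimates, their intervals or treatment.

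The conclusion rests on the Synopsis alone. Asking whether Section 10 gives the reference values, the data cut and the handling of SD seen before day 84 is a reasonable low-priority query. A cohort with 2 or fewer responders is most clearly reported as not meeting the ORR criterion, with any decision to go on described as exploratory.

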Cohort 2: AMG 479 18 mg/kg plus AMG 655 3 mg/kg IV on day 1 of each Q3W cycle

Cohort 3: AMG 479 18 mg/kg plus AMG 655 15 mg/kg IV on day 1 of each Q3W cycle

There will be no intra-subject dose escalations in each of the planned dose cohorts. Alternative AMG 655 doses (eg, 0.3 mg/kg IV) and/or AMG 479 doses may be explored based on safety and PK data.

Part 2: AMG 479 18 mg/kg plus AMG 655 at the dose selected in Part 1 (up to 15 mg/kg) IV on day 1 of each Q3W cycle

AMG 655 and AMG 479 will be administered through a peripheral line or indwelling catheter using a nonpyrogenic, low protein binding filter with a 0.2- or 0.22-micron pore size in-line filter infusion set-up.

Control Group: There is no control group.

Key Study Procedures: See [Section 7.1](#) and Schedule of Assessments ([Appendix A](#)) for details.

Screening Procedures

- Review of inclusion and exclusion criteria
- Medication and medical history, concomitant medications/treatment(s), adverse events
- Vital signs: resting pulse, respiration, blood pressure, and temperature
- Physical examination, including height and weight
- ECOG performance status assessment
- Laboratory tests; including hematology, chemistry, coagulation, urinalysis, pregnancy test
- Submission of formalin-fixed, paraffin-embedded tumor tissue (paraffin tumor block, or slides) and associated pathology reports (Required for subjects with CRC, ovarian cancer, and sarcoma; optional, if tumor tissue is available, for subjects with NSCLC and pancreatic cancer).
- 12-lead electrocardiogram (ECG)
- Radiological imaging to assess disease extent (CT scan or MRI of the brain, chest, abdomen, and all other sites of disease; within 28 days prior to enrollment)

Treatment and Follow-up Procedures

- Recording of adverse events and concomitant medications
- Vital signs: resting pulse, respiration, blood pressure, and temperature
- Physical examination, including weight, and ECOG performance status assessment
- Laboratory tests; including hematology, chemistry, pregnancy test
- Samples for biomarkers and anti-AMG 655 and anti-AMG 479 antibodies
- Samples for AMG 655 and AMG 479 PK
- ECG
- Radiological imaging to assess disease extent (CT scan or MRI [same modality throughout the study] of the chest, abdomen, and all other sites of disease [except: brain imaging only as clinically indicated] every 6 weeks [\pm 7 days] during the first 6 months of the study, and every 9 weeks [\pm 7 days] thereafter)

Approved

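### Does the Part 2 rule of at least 3 responses in 15 need a safety condition, and a threshold or label for cohorts that miss it?

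*Combined protocol and SAP*

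**What the plan says.** Under Study Hypotheses, Part 2, the synopsis expects that the combination "will have an acceptable safety profile and will be associated with at least 3 objective responses"; the count is taken among 15 evaluable patients and must be reached in one or more of the cohorts.

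Under Statistical Considerations, Part 2, tumor types for further study are identified "using the following criterion: at least 3 out of 15 subjects have an objective response", which the plan equates to a response rate of at least 20%. A second route follows: "If 2 or less responders are observed in a given cohort, then all other parameters of clinical benefit" (clinical benefit rate and PFS are named, and the list is left open) "and of patient safety will be evaluated to determine if further study is warranted".

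The same section says "All safety data collected in part 2 of the study will be summarized per cohort and in aggregate over all cohorts". It schedules safety reviews after at least 15 and 45 Part 2 subjects have completed one cycle, with more as warranted. It also commits to each cohort's objective response rate with an exact 95% confidence interval.

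PFS is a secondary endpoint. Clinical benefit rate is exploratory ("To estimate the efficacy of AMG 655 in combination with AMG 479 using clinical benefit rate"). On comparison, the synopsis states: "There is no control group". It refers to Section 10 for statistical detail. Section 10 was not in the text available here, so what follows concerns the synopsis only.

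**The concern.** Two things look wrong.

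First, the hypothesis joins safety to the response count, while the selection criterion gives the count alone and the decision text brings safety in only at 2 or fewer responders. Read literally, a cohort with 3 responders qualifies on response alone and a cohort with 2 has its safety examined, which is an odd asymmetry.

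Second, the review of cohorts with 2 or fewer responders has no cut-off and an open list of parameters. It draws on secondary and exploratory measures in about 15 uncontrolled subjects. Nothing in the synopsis says that a tumor type advanced this way will be described differently from one that met 3/15. A finding that further study is warranted could then mean either that a prespecified count was reached or that a judgment was made. The 3/15 figure would not by itself determine how often an inactive tumor type goes forward.

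**Working it through.** **The plan's own figures.** 3/15 = 20.0%, and 6 cohorts × 15 = 90 subjects. Both agree with the synopsis.

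**How often the second look is reached.** Let X be the number of responders in a cohort, X ~ Binomial(15, p). Then P(X ≤ 2) = (1−p)^15 + 15p(1−p)^14 + 105p²(1−p)^13. At p = 0.20 this is 0.0352 + 0.1319 + 0.2309 = 0.3980. The 20% rate is the plan's; 5% and 10% are assumptions, because the synopsis gives no reference rate.

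| True response rate | P(X ≥ 3) | P(X ≤ 2) | Expected cohorts of 6 with X ≤ 2, if all share the rate |
|---|---|---|---|
| 5% | 3.6% | 96.4% | 5.8 |
| 10% | 18.4% | 81.6% | 4.9 |
| 20% | 60.2% | 39.8% | 2.4 |

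So the second look is not a rare branch.

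**What it could add.** If a share s of cohorts with X ≤ 2 were advanced, the overall chance of advancing is P(X ≥ 3) + s × P(X ≤ 2).

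- s = 0.10: 0.0362 + 0.0964 = 13.3% at a 5% rate; 0.1841 + 0.0816 = 26.6% at 10%; 0.6020 + 0.0398 = 64.2% at 20%.
- s = 0.25: 27.7%, 38.8% and 70.1% respectively.

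These figures depend wholly on s, which is invented. They also hold s constant across true response rates, as if the review of clinical benefit and PFS carried no information. A review with any discrimination would advance fewer inactive cohorts than active ones. A reporting label would leave every one of these numbers unchanged.

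**Why a judgment step is reasonable.** The exact (Clopper-Pearson) 95% intervals are 1.7% to 40.5% for 2/15 and 4.3% to 48.1% for 3/15. They overlap almost entirely, and both contain 20%. One responder is a thin basis for an automatic stop.

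**Can a reader tell which route was taken?** Yes. The count and interval are reported for every cohort and the cut-off is in the protocol. A cohort reported at 2/15 visibly did not meet it.

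**The two safety statements side by side.** In the hypothesis, the grammatical subject is the combination, and the phrase about at least one cohort attaches to the responses. The criterion under Statistical Considerations has a narrower job, which is to pick tumor types. Read together, they give one safety judgment on the combination and a response screen for each tumor type. That is not a contradiction. Naming safety in the second branch does not remove it from the first: the scheduled reviews and the safety summaries cover all Part 2 subjects whatever their response.

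**The case for a change.** The strongest case for a change is that the interim safety reviews do not supply the missing condition. They are triggered by total Part 2 enrollment, not by cohort, and the only stated consequence concerns enrollment. The safety summaries are descriptive, and acceptable safety is not defined. Nothing formally ties either to the decision on further study. On the second look, two sentences would cost nothing and would keep judgment visibly apart from a met criterion.

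The textual observation stands: the synopsis does not say whether safety is judged once for the combination or cohort by cohort, and the literal asymmetry is real. The inference of harm does not. A sponsor deciding on further study will have the cohort and aggregate safety summaries in hand, and nothing in the plan tells it to disregard them. On the second look, the plan openly prespecifies the discretion: its trigger, two of its measures and its purpose. The 3/15 criterion is itself an observed count in an uncontrolled cohort, with no hypothesis test stated in the synopsis. The contrast between a met criterion and descriptive evidence is therefore weaker than it sounds.

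**Conclusion.** No change follows. The safety point is a looseness of wording in a synopsis, with a natural consistent reading and with safety already reviewed and summarized across all of Part 2. The second look is a fair trade-off for an estimation study with 15 subjects per cohort: treating 3/15 as binding would reject 39.8% of cohorts with a true response rate of 20%. A label would add little, since each cohort's response count is reported against a published cut-off.

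The effect on sample size, data, estimates and intervals is nil. The higher chances of advancing an inactive tumor type (for example 13.3% or 27.7% at a 5% rate, against 3.6% for 3/15 alone) rest on assumed advancement shares and on assumed response rates. They do not breach any error rate stated in the synopsis, which gives no null rate, alpha or power. This conclusion covers the synopsis; Section 10 may already give the detail.

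### The Part 2 primary analysis may be cut at 12 weeks, the nominal second scan, before late-enrolled subjects' responses can be confirmed; the piecewise option is most exposed

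*Combined protocol and SAP*

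**What the plan says.** All of the following is in the Protocol Synopsis.

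- **Trigger** (Statistical Considerations, Part 2): the primary analysis is "planned to occur after all subjects have had the opportunity to complete 4 cycles of treatment".
- **Cycle length** (Study Design, Parts 1 and 2): "AMG 655 and AMG 479 treatment will be administered Q3W until disease progression" or another stopping reason.
- **Scans** (same section): "Radiological imaging (per modified RECIST) will be performed every 6 weeks", with a window of 7 days either side, for the first 6 months.
- **Endpoint**: the Part 2 primary endpoint is the rate of confirmed CR or PR by modified RECIST, assessed by the local investigator.
- **Criterion for further study**: at least 3 responders among the 15 subjects of a cohort. Below that, the rule is soft: "If 2 or less responders are observed in a given cohort, then all other parameters of clinical benefit", together with safety, are weighed.
- **Piecewise option**: if recruitment is uneven, "a piecewise approach to the primary analysis may be taken with the analysis for the quickest recruiting cohorts occurring first".
- **Cohorts**: "Enrollment into the 6 cohorts will occur in parallel, independent of one another".
- **Final analysis**: it follows once all subjects have progressed, died or left the study.

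The pages available give neither a confirmation interval nor a rule for a response still awaiting confirmation at the cut. They refer to Section 10 for details, and Section 10 is not among them.

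**The concern.** The trigger is counted in treatment cycles, but the endpoint depends on scans, and the two do not line up. The minimum follow-up ends at about the second scan, while confirmation needs a scan after the one that first shows response.

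The resulting error goes one way. A pending response counts as no response, so confirmed ORR can only be understated. With a threshold of 3 in 15, one pending response is enough to take a cohort from 3/15 (20.0%, exact 95% CI 4.3 to 48.1%) to 2/15 (13.3%, 1.7 to 40.5%).

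The piecewise option adds to this. Under a single cut for all six cohorts, the faster ones gain follow-up while the slowest finishes enrolling. Analysing a fast cohort on its own removes that extra time, and a fast cohort also has the largest share of subjects enrolled shortly before its cut.

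**Working it through.** **The plan's own figures.** 3/15 = 20% and 6 × 15 = 90 subjects, both as stated. The pages give no null rate, alpha or power to reproduce.

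**Timing.**
- Minimum follow-up: 4 cycles × 3 weeks = 12 weeks.
- Scan windows: scan 1 at weeks 5–7, scan 2 at 11–13, scan 3 at 17–19, scan 4 at 23–25.
- With confirmation at the next scheduled scan, a response first seen at scan 1 is confirmed at weeks 11–13, and one first seen at scan 2 at weeks 17–19.
- A subject enrolled at least 19 − 12 = 7 weeks before the last subject has passed scan 3 by the cut. For responses first seen at scan 1 or 2, only the last 7 weeks of enrolment are therefore affected. For responses first seen at scan 3, the reach is 25 − 12 = 13 weeks.

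**Assumptions for the size of the effect (none is in the documents).** True confirmed ORR 30%; first response at scans 1/2/3 in 60/30/10% of responders; confirmation at the next scheduled scan; scan dates uniform within the window; uniform accrual; cut exactly at the minimum.

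**Formula.** For a subject with follow-up *t*, the share of eventual confirmed responses already confirmed is

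c(t) = 0.6·P(scan 2 ≤ t) + 0.3·P(scan 3 ≤ t) + 0.1·P(scan 4 ≤ t).

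For the last-enrolled subject, t = 12 and c = 0.6 × 0.5 + 0 + 0 = 0.30. With full follow-up, c = 1 and P(X ≥ 3 | n = 15, p = 0.30) = 0.873.

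**Piecewise cut** (simulation of cohorts of 15; cut = that cohort's last enrolment + 12 or + 19 weeks):

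| Cohort accrual (weeks) | Mean subjects in last 7 weeks | Responses captured at 12 weeks | P(≥3/15), 12 weeks | P(≥3/15), 19 weeks |
|---|---|---|---|---|
| 6 | 15 | 56% | 0.476 | 0.822 |
| 12 | 9.7 | 70% | 0.637 | 0.847 |
| 26 | 5.0 | 83% | 0.763 | 0.859 |
| 52 | 3.0 | 89% | 0.810 | 0.865 |

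A hand check treats the observed rate as 0.30 × share captured. For 6 weeks that is 0.30 × 0.56 = 0.168, and P(X ≥ 3 | 15, 0.168) = 0.473, close to the simulated 0.476.

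**Common cut** (last enrolment in any cohort + 12 weeks):
- All six cohorts accruing over 26 weeks: 0.793 each.
- Accrual over 12/20/28/36/44/52 weeks: 0.873/0.873/0.874/0.871/0.858/0.811.
- With + 19 weeks: 0.862–0.864 and 0.864–0.873 respectively.

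**Sensitivity.**
- Earlier responses (80/20% at scans 1/2), 12 weeks: piecewise 0.685/0.773/0.819/0.837 for 6/12/26/52 weeks; common cut with 26-week accrual 0.839. At 19 weeks all return to 0.87.
- Confirmation allowed 4 weeks after first response, by a scan outside the stated schedule, 60/30/10 pattern: piecewise at 12 weeks about 0.62/0.73/0.81/0.83.

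**The case against.** The strongest reply is that the problem arises only if the sponsor chooses it. The word *after* sets a minimum, so a later cut is allowed, and the piecewise route is optional and conditional on uneven recruitment. Under a common cut with uneven accrual, five of six cohorts lose almost nothing. This stands, and it is why the point is graded low. But nothing in the pages requires a later cut, and the trigger is the only safeguard they state.

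Second, Section 10 and the modified RECIST details may already define the confirmation interval, evaluability or the handling of pending responses. This also stands: what is said here about missing rules applies to the synopsis alone.

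Third, falling below 3 of 15 does not drop a tumour type. Wider review follows, an open-label team may well see a pending response, and a final analysis comes later. So the probabilities above are chances of meeting the criterion at the primary analysis, not of continuing development. The review is not wholly independent of the cut, though. Clinical benefit rate counts stable disease of at least 12 weeks, which a late subject scanned in weeks 12–13 cannot yet show. The final analysis waits until every subject has progressed, died or left.

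Fourth, the sizes depend on assumed response timing, accrual and confirmation rule. The 48% needs a whole cohort enrolled in 6 weeks. If confirmation after 4 weeks is allowed, a week-6 response is always confirmable by 12 weeks (at most 7 + 4 = 11), and the loss shrinks. It does not vanish: a scan-2 response would still be confirmed no earlier than week 11 + 4 = 15.

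**Conclusion.** The concern holds as a possibility that the plan leaves open. A cut at the earliest permitted date leaves scan-2 responses in late-enrolled subjects unconfirmed, and some week-6 responses too if confirmation waits for the next scheduled scan. It biases the confirmed count downward.

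Under the assumptions listed, the chance of reaching 3 of 15 falls from 87% to between 48% (6-week accrual) and 81% (52-week accrual) when a cohort is analysed piecewise. Under a common cut it is 79% in every cohort if accrual is even over 26 weeks. If accrual is uneven, the loss is material only in the slowest cohort (81%).

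The direction follows from the documents; the size depends on the assumed inputs. Because the criterion is soft and a final analysis follows, the cost is a weaker primary readout rather than a wrong final decision. This is a cheap improvement, held with moderate confidence because Section 10 could not be read.

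**What to change.** Replace the four-cycle trigger, in the synopsis and in Section 10, with a scan-based one. Suggested text: *The primary analysis, including each cohort's analysis under the piecewise approach, takes place once every subject in the analysed set has had the opportunity to complete the week-18 scan including its 7-day window (19 weeks from study day 1), or has progressed, died or withdrawn earlier.*

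Under the same assumptions, this raises the chance of reaching 3 of 15 to 82–86% piecewise and 86–87% with a common cut. The remaining shortfall comes from responses first seen at scan 3; with the 80/20 pattern there is none.

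The cost is one sentence in each place and a readout up to 19 − 12 = 7 weeks later. It needs no extra scans, visits or subjects. A rule for reporting and updating pending responses would avoid the delay, but the primary estimate would remain provisional. If Section 10 already ties the cut to confirmatory scans, only the synopsis needs aligning.
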